Appendix D. Details of Supplementary Analyses for Ranked Secondary Continuous Endpoints

Tipping Point Analysis for Key Secondary Non-Radiographic Continuous Endpoints

To assess the impact of potential departures from the missing-at-random assumption, tipping point analyses are conducted as a sensitivity check for change from baseline in key secondary non-radiographic continuous endpoints at the protocol defined primary time point.

The tipping point analyses are two-dimensional, i.e., assumptions about the missing outcomes on the upadacitinib treatment groups and the placebo group are allowed to vary independently. In addition, the focus is on scenarios where missing outcomes on upadacitinib are worse than the imputed values on upadacitinib, while missing outcomes on placebo are better than the imputed values on placebo. Missing values are first imputed via MI under MAR (where the MI imputation is performed upon AO data), and then a shift parameter is applied to the imputed values (a different shift parameter may be specified for each treatment group). This is implemented by PROC MI using the MNAR statement.

More specifically, PROC MI using the fully conditional specification (FCS) method will be performed to impute any missing value and therefore does not rely on a monotone missing pattern. In fact, the FCS method can handle any arbitrary missing data pattern. Treatment is included in the FCS imputation model to enable sampling conditional on treatment groups. Additionally, the imputation model includes stratification factor of current use of non-biologic DMARD (yes/no), gender, race (white vs. non-white), age, baseline BMI, geographic regions, duration of PsA diagnosis and the baseline value of the endpoints of interest, as well as longitudinal response observed at any other visits. The SAS code example is as follows:

For a given pair of shift parameters, the SAS code example is as follows:

```
PROC MI DATA=DATA_WIDE OUT=DATA_WIDE_BOUNDED NIMPUTE=20
SEED=12345;

CLASS TRTP &COVCAT;
FCS;
By trtp;
VAR &COVCON &COVCAT WEEK_2 WEEK_4 WEEK_8 WEEK_12;
MNAR ADJUST (WEEK_12 / SHIFT=&SJ1
ADJUSTOBS=(TRTP='PLACEBO'));
MNAR ADJUST (WEEK_12 / SHIFT=&SJ2 ADJUSTOBS=(TRTP='UPA 15MG'));
RUN;
```

Note: The input dataset is in wide format. TRTP denotes the treatment group. &COVCON denotes baseline continuous covariates including baseline age, baseline BMI, duration of PsA diagnosis and baseline value of the endpoint of interest. &COVCAT denotes categorical covariates including current use of non-biologic DMARD, gender, race, and regions. WEEK_2, WEEK_4, WEEK_8, WEEK_12 denote the observed values at each visit. &SJ1and &SJ2 denote the shift parameters for the placebo group and upadacitinib 15 MG group respectively.

In cases where the shifted values are smaller than the minimum or larger than maximum value of the endpoint, (i.e., out of range), the minimum or maximum value of the endpoint is used in further analysis steps. For each pair of shift parameters, the SAS procedure PROC MIXED is used for ANCOVA analysis with Huber-White sandwich errors which includes the fixed effects of treatment, the stratification factor of current DMARD use and the continuous fixed covariate of baseline measurement on each of the multiple imputed datasets to obtain the results for each upadacitinib treatment group versus the placebo group comparison. These results will be aggregated using Rubin's method to get p-values.

If one pair of shift parameters are found to just reverse the study conclusion, in terms of p-value larger than 0.05 (the original p-value < 0.05), then the shift parameters are identified as the tipping point. The results for a grid of shift parameter combinations are provided in tabular format.

The SAS code example of the data imputation step for tipping point analysis using MI is provided above. The SAS code example for the analysis and results combination step using PROC MIXED and PROC MIANALYZE is as follows:

```
PROC MIXED DATA=ALL EMPIRICAL;
```

```
ODS OUTPUT LSMEANS=MIXEDLSMEANS DIFFS=DIFF;
    BY Shift1 Shift2 IMPUTATION;
    CLASS TRTP STRATA USUBJID;
    MODEL CHG = BASELINE TRTP STRATA / SOLUTION;
    LSMEANS TRTP / CL PDIFF DIFF;
    Repeated/subject = USUBJID;
RUN;
DATA DIFF1;
    SET DIFF;
    COMPARISON= TRTP||' VS '||LEFT( TRTP);
RUN;
PROC SORT DATA=DIFF1; BY COMPARISON Shift1 Shift2 IMPUTATION; RUN;
PROC MIANALYZE DATA=DIFF1;
    ODS OUTPUT PARAMETERESTIMATES=GROUP OUTPUT;
    BY comparison shift1 shift2;
    MODELEFFECTS ESTIMATE;
    STDERR STDERR;
RUN;
/* Comparison of "UPA 15 mg" vs. "Placebo" */
data miparm1;
set GROUP OUTPUT;
if comparison='1
                           VS
                                          2' then output miparm1;
proc transpose data=miparm1 (keep= Shift1 Shift2 Probt)
out=wide miparm1;
by shift1;
id shift2;
var Probt;
run:
```

Note: The input dataset ALL includes all (# of shift1 parameters) * (# of shift2 parameters) * (# of imputations in MI) imputed datasets. TRTP denotes the treatment group and STRATA denotes the stratification factor used in analysis. CHG denotes the change from baseline value and BASELINE denotes the baseline value.

[figure not shown]
MI Analysis for Radiographic Continuous Endpoints

The MI analysis will impute missing data multiple times under appropriate random variation and thus generate multiple imputed "pseudo-complete" datasets. The imputation assumes of missing at random (MAR). ANCOVA will be performed on each of the multiple imputed datasets. The results will be aggregated across the multiple imputed datasets using Rubin's method. The SAS procedure PROC MI with the monotone

statement and REGRESSION method is used. Before applying PROC MI, MCMC is applied where necessary to augment data into monotone missing pattern. The SAS code example for PROC MI is as follows:

PROC MI DATA=DATA WIDE OUT=OUTMI NIMPUTE=1 SEED=12345;

[figure not shown]
```
Mcmc impute = monotone;
      VAR &COVCON base aval;
       By trtp;
RUN:
PROC MI DATA=DATA WIDE OUT=OUTMI NIMPUTE=20 SEED=12345;
      CLASS &COVCAT;
     MONOTONE;
      VAR &COVCON &COVCAT base aval;
       By trtp;
RUN:
       The input dataset is in wide format. TRTP denotes the treatment group. &COVCON denotes baseline
Note:
       continuous covariates including baseline age, baseline BMI, duration of PsA diagnosis and baseline value of
       the endpoint of interest. &COVCAT denotes categorical covariates including current use of non-biologic
       DMARD, gender, race and regions. WEEK 16, WEEK 24 denote the observed values at each visit.
PROC MIXED DATA=ALL;
    ODS OUTPUT LSMEANS=MIXEDLSMEANS DIFFS=DIFF;
    BY IMPUTATION ;
    CLASS TRTP STRATA;
    MODEL CHG = BASELINE TRTP STRATA / SOLUTION;
    LSMEANS TRTP / CL PDIFF DIFF;
RUN:
DATA DIFF1;
    SET DIFF;
    COMPARISON= TRTP||' VS '||LEFT( TRTP);
RUN;
PROC SORT DATA=DIFF1; BY COMPARISON IMPUTATION ; RUN;
PROC MIANALYZE DATA=MIXEDLSMEANS1;
ODS OUTPUT PARAMETERESTIMATES=GROUP OUTPUT;
BY TRTP;
MODELEFFECTS ESTIMATE;
```

```
STDERR STDERR;
RUN;

PROC MIANALYZE DATA=DIFF1;
    ODS OUTPUT PARAMETERESTIMATES=GROUP_OUTPUT;
    BY comparison;
    MODELEFFECTS ESTIMATE;
    STDERR STDERR;
RUN;
```

Note: The input dataset ALL includes all 20 imputed datasets. TRTP denotes the treatment group and STRATA denotes the stratification factor used in analysis. CHG denotes the change from baseline value and BASELINE denotes the baseline value.

Appendix E. Exposure Adjusted AE Rate Difference and Normal Approximation Based 95% Confidence Interval⁶

[figure not shown]
Assume the occurrence of TEAE of special interest follows a Possion distribution and let λ denote the rate of occurrence of TEAE under the total exposure time for a treatment group. Let n_1 and n_2 be the number of AEs reported in an upadacitinib dose group and the combined placebo group, respectively. Let T_1 and T_2 be the total number of days exposed to study drug summed across all treated subjects in an upadacitinib dose group and the combined placebo group. Under the assumption that n_1 and n_2 follow independent Possion distribution with parameters $\lambda_1 T_1$ and $\lambda_2 T_2$, the $\hat{\lambda}_1 = n_1/T_1$ and $\hat{\lambda}_2 = n_2/T_2$. So the exposure adjusted TEAE rate difference can be estimated by

$$\theta = \hat{\lambda}_1 - \hat{\lambda}_2$$

Using normal approximation, the 95% confidence interval can be calculated by

$$\hat{\lambda}_1 - \hat{\lambda}_2 \pm Z_{\alpha/2}\hat{\sigma}$$

Where
$$\hat{\sigma} = \sqrt{n_1/T_1^2 + n_2/T_2^2}$$

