9.1.2 Handling of Missing Data and Intercurrent Events

Non-Responder Imputation (NRI) Approach

The NRI approach will handle data for binary endpoints as follows.

- Subjects who prematurely discontinue from study drug will be considered as non-responders for all subsequent visits after discontinuation.
- In addition, any subject with any missing value for the binary endpoints at a specific visit will be treated as non-responder for that visit.

NRI data handling will be used for the primary estimand (refer to Section 9.2.1) for the binary endpoints.

Mixed-Effects Model Repeated Measures (MMRM) Up to Week 24

The repeated measure analysis will be conducted using mixed models including observed data at all visits. For the MMRM analysis, data collected after premature discontinuation

of study drug will be excluded. The mixed model includes the categorical fixed effects of treatment, visit, treatment-by-visit interaction, the stratification factor current DMARD use (yes/no) and the continuous fixed covariates of baseline measurement. An unstructured variance covariance matrix will be used. The parameter estimations are based on the assumption of data being missing at random (MAR) and using the method of restrictive maximum likelihood (REML). MMRM will be used for the primary estimand of the non-radiographic continuous endpoints (refer to Section 9.2.3).

[figure not shown]
Linear Extrapolation for Radiographic Data

For radiographic data (i.e., SHS-based endpoints), linear extrapolation will be applied to subjects with missing data including those due to premature discontinuation of study drug or meeting the rescue criteria, where the missing x-ray at the time point of interest will be imputed assuming a linear relationship across visits. Linear extrapolation will be used to facilitate the primary estimand for radiographic endpoints (refer to Section 9.2.3). Linear extrapolation will not be provided for Week 104 analysis and future analyses.

As Observed (AO)

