The AO data handling will not impute values for missing evaluations, and thus a subject who does not have an evaluation on a scheduled visit will be excluded from the AO analysis for that visit. Regardless of premature discontinuation of study drug or use of rescue medication, all observed data will be used in the analysis. The AO data handling will be used to facilitate the supplementary analysis for both binary and continuous endpoints including radiographic endpoints (refer to Section 9.2.2 and Section 9.2.3 where the corresponding supplementary estimands for the primary and ranked secondary endpoints are described respectively).

The intention-to-treat (ITT) principle for the analysis using AO data, AO (with imputation), where additional missing data will be imputed as non-responders, will be used for the supplementary analysis of the primary and key secondary binary endpoints. AO with imputation will not be provided for Week 104 analysis and future analyses.

Mixed Effect Model Repeat Measurement (MMRM) and Generalized Linear Mixed Model (GLMM) for Long-Term Analysis

[figure not shown]
The repeated measure analysis will be conducted using mixed model including As Observed measurements at all visits. MMRM will be used for continuous endpoints and GLMM will be used for non-radiographic binary endpoints. The mixed models will include the categorical fixed effects of treatment, visit and treatment-by-visit interaction, and stratification factor current DMARD use (yes/no). The categorical fixed effect of subject's discontinuation status may also be included in the model as appropriate. For the MMRM analysis of change from baseline in continuous endpoints, the baseline measurement will be included as a continuous fixed covariate. Unstructured, Toeplitz, compound symmetry, or other covariance structures may be considered.

9.2 Efficacy Analysis through Week 24

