For ACR20 response at Week 12, analysis will be conducted to assess the non-inferiority of each upadacitinib dose versus adalimumab on the placebo-subtracted treatment difference using Koch's 3-arm test statistic as described in Appendix C. The test aims to show that upadacitinib preserves at least 50% of the placebo-subtracted adalimumab effect. If statistical significance is achieved for the non-inferiority assessment, superiority of upadacitinib versus adalimumab will be tested for ACR20 subsequently as described in Section 9.2.5.

Non-Radiographic Continuous Endpoints

For non-radiographic continuous endpoints, the estimand is the difference in mean change from baseline at the protocol defined time point (e.g., HAQ-DI at Week 12) under the assumption that patients with missing data, including those due to premature discontinuation of study drug, can have their measurements at the protocol defined time point predicted by their observed data and the observed data for other patients for their respective assessments during follow-up. The comparison is for each upadacitinib dose group vs placebo for patients randomized and treated with at least one dose of study drug.

To analyze the primary estimand for the continuous ranked secondary efficacy endpoints, statistical inference will be conducted using the MMRM model and the associated data handling as described in Section 9.1.2, with fixed effects of treatment, visit, treatment-by-

[figure not shown]
visit interaction, the stratification factor of current DMARD use (yes/no) and the continuous fixed covariate of baseline measurement. The LS mean and 95% CI for each randomized treatment group and the LS mean treatment difference, the associated 95% CI and the p-value between each upadacitinib dose group and the combined placebo group will be provided. For change from baseline in Patient's Assessment of Pain NRS and change from baseline in HAQ-DI at Week 12, superiority of upadacitinib vs. adalimumab will also be tested using the same MMRM model.

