The supplementary analysis for ranked non-radiographic secondary continuous endpoints will be conducted using AO data handling and using the analysis of covariance (ANCOVA) model with treatment and the stratification factor of current DMARD use (yes/no) as the fixed factors and the corresponding baseline values as the covariates. The corresponding estimand is the difference in the mean change from baseline in the efficacy endpoints at the protocol defined time point regardless of treatment discontinuation or use of rescue medication, comparing each upadacitinib dose group vs placebo. The analysis will be conducted for those who are randomized, received study drug and have the efficacy measurement at the protocol defined time point.

For the key continuous endpoint change from baseline in HAQ-DI at Week 12, tipping point analysis will also be conducted using multiple imputation (MI) as additional supplementary analysis to explore various missing data assumptions including missing not at random (MNAR). Details of the tipping point analysis for continuous endpoints are outlined in Appendix D.

Radiographic Endpoints

For change from baseline in SHS at Week 24, statistical inference will be conducted using ANCOVA model and the associated data handling as described in Section 9.1.2 with treatment and the stratification factor of current DMARD use (yes/no) as the fixed factors and the corresponding baseline values as the covariates. The primary estimand for the x-ray assessment is the difference in the mean change from baseline in SHS score at Week 24, under the assumption that patients with missing data, including those due to

premature discontinuation of study drug or use of rescue medication, can have their measurements at Week 24 predicted using their SHS score from the baseline window and the Week 16 window. The comparison will be between each upadacitinib dose group vs placebo for patients randomized and treated with at least one dose of study drug.

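### The HAQ-DI Week 12 tipping-point analysis starts from as-observed data, so it leaves untested the MAR assumption that the primary MMRM makes for subjects assessed after stopping study drug

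*SAP*

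**What the plan says.** **Primary analysis.** SAP section 9.1.2 sets the MMRM data rule in one sentence: "For the MMRM analysis, data collected after premature discontinuation" "of study drug will be excluded". It adds: "The parameter estimations are based on the assumption of data being missing at random (MAR"). Section 9.2.3 defines the estimand for non-radiographic continuous endpoints "under the assumption that patients with missing data, including those due to premature discontinuation of study drug, can have their measurements" predicted from observed data. Outcomes after stopping drug are therefore replaced, in effect, by a MAR prediction.

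**As-observed handling.** Section 9.1.2 says of AO data: "Regardless of premature discontinuation of study drug or use of rescue medication, all observed data will be used in the analysis".

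**Tipping point.** Appendix D gives the purpose: "To assess the impact of potential departures from the missing-at-random assumption, tipping point analyses are conducted as a sensitivity check". It gives the data set as "Missing values are first imputed via MI under MAR (where the MI imputation is performed upon AO data"), and then adds a shift to the imputed values. The grid is two-dimensional, with upadacitinib made worse and placebo better. Out-of-range values are reset to the scale limits, and a result has tipped once p exceeds 0.05. Section 9.2.3 describes the same analysis for HAQ-DI at Week 12 differently: "tipping point analysis will also be conducted using multiple imputation (MI) as additional supplementary analysis to explore various missing data assumptions".

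**Follow-up.** Protocol section 5.4.1 asks subjects who stop study drug to keep attending scheduled visits, so off-drug Week 12 HAQ-DI values are expected by design.

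**The concern.** A subject who stops drug before Week 12 but attends that visit is handled in two ways. The MMRM discards the Week 12 value and predicts it under MAR. The tipping-point analysis keeps it as observed and never shifts it. Off-drug values at earlier visits also enter the imputation model for subjects who are truly missing.

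The usual reading of a tipping point is that zero shift stands for the primary assumption, and that the distance to the tip measures how far the assumption can fail. Here zero shift stands for a different estimand, and the shift reaches only part of the set that the MMRM treats as MAR. No other section of the SAP gives a missing-not-at-random analysis on the MMRM data set, and protocol section 8.1.4.5 makes such a model optional. At stake is whether the first ranked secondary endpoint has a sensitivity analysis aligned with its primary estimand.

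**Working it through.** **No plan figure to reproduce.** The documents give no HAQ-DI effect size, SD, tipping point or count of off-drug Week 12 values. What follows shows how the two versions relate and illustrates the size.

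**Handling by type of subject at Week 12**

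| Subject | Primary MMRM | Tipping point as planned |
|---|---|---|
| On drug, assessed | Observed | Observed |
| Not assessed | MAR | Imputed, then shifted |
| Stopped drug, assessed | Excluded, MAR | Observed, not shifted |

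The versions differ directly in the last row. Week 16 rescue plays no part, because the Week 12 window in SAP Table 1 closes at Day 99 and the Week 16 target is Day 113.

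**Inputs**
- From the documents: 410 per upadacitinib arm; combined placebo 205 + 205 = 410; tipping at p > 0.05, hence 1.96; HAQ-DI range 0 to 3 (SAP section 9.4.9).
- Assumed: D, the effect under MAR; q, the share of the upadacitinib arm that the MMRM drops (10% borrows the planning dropout rate); s, the share of those with an observed off-drug value; g, how much worse those values are than their MAR prediction.

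**Formulas**, shifting upadacitinib only, ignoring truncation and the effect of imputation on the standard error:
- All values that the MMRM drops are shifted: T_M = (D - 1.96 × SE) / q
- Plan as written: T_AO = (D - q × s × g - 1.96 × SE) / (q × (1 - s)) = (T_M - s × g) / (1 - s)

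If g = 0, the ratio is 1/(1-s): 1.33, 2 and 4 for s = 25%, 50% and 75%. If s = 0, the two are equal. T_AO falls below T_M once g exceeds T_M.

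**In SD units**, D = 0.4, q = 10%: SE = sqrt(2/410) = 0.0698, so T_M = (0.4 - 0.1369)/0.10 = 2.63.

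| s | g | T_AO | T_AO / T_M |
|---|---|---|---|
| 25% | 0.4 | 3.37 | 1.28 |
| 50% | 0.4 | 4.86 | 1.85 |
| 75% | 0.4 | 9.32 | 3.54 |
| 50% | 3 | 2.26 | 0.86 |

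Reversal comes sooner with a smaller effect: at D = 0.26, q = 10%, s = 50% and g = 1.5, T_AO is 0.96 against T_M of 1.23.

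A small simulation of multiple imputation with sandwich-error ANCOVA (25 runs per setting, 10 imputations, D = 0.4, q = 10%) gave median shifts, AO against MMRM set, of 4.8 and 2.8 for s = 50%, g = 0.4, and 3.2 and 2.5 for s = 25%, g = 0.4.

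**In HAQ-DI units**, assuming a difference of 0.25, SD 0.5 and g = 0: SE = 0.5 × sqrt(2/410) = 0.0349, and 0.25 - 1.96 × 0.0349 = 0.1816.
- 10% shifted: 0.1816/0.10 = 1.82
- 5% shifted (s = 50%): 0.1816/0.05 = 3.63
- 3% shifted (s = 70%): 0.1816/0.03 = 6.05

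With equal and opposite shifts and equal missingness in both arms, these halve to 0.91, 1.82 and 3.03.

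**The case against.** The strongest defence is that the SAP never ties this analysis to the MMRM alone. Section 9.2.3 calls it supplementary and places it directly after the AO ANCOVA. Appendix D is titled as supplementary analyses and uses ANCOVA covariates. Appendix B also uses AO data for the ACR20 tipping point, so the choice looks deliberate. Read that way, it tests truly missing values under the AO estimand, and a larger shift is legitimate because fewer values are missing. This stands as a description of what the analysis does. It does not fit the purpose stated in Appendix D, a sensitivity check on MAR, because the planned primary analysis that rests on MAR is the MMRM.

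A reader might infer more than the documents support:
- **That MAR is not stressed at all.** Values truly absent at Week 12 are missing in both versions and are shifted.
- **That outcomes after discontinuation are never examined.** The AO ANCOVA in section 9.2.3 uses them, although it does not shift the primary estimand.
- **That robustness is certainly overstated.** The direction depends on g and s, and can reverse.
- **That the result would always look untippable.** Under the assumed inputs an upadacitinib-only shift of 3.63 or 6.05 exceeds the 0 to 3 scale. The planned grid also moves placebo, which lowers the shift needed per arm. One assumed scenario cannot carry the word always.

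**Conclusion.** The mismatch is in the text. The HAQ-DI tipping point addresses the estimand regardless of discontinuation. It leaves untested the MMRM's MAR assumption for subjects who stopped drug and were still assessed at Week 12, so its tipping shift should not be reported as robustness of the primary HAQ-DI result.

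The size cannot be fixed from the documents. The planned version will usually need a larger shift than an MMRM-consistent one: twice as large if half of the dropped subjects have off-drug values that match their MAR prediction. It needs a smaller shift if those values are worse than predicted by more than the MMRM-consistent tipping shift. If nobody stops drug and still contributes HAQ-DI, there is no effect. The HAQ-DI figures rest on an assumed effect, SD and shares, and ignore truncation.

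A reader might also infer bias in the primary test or loss of type I error control. Neither follows: the MMRM and the multiple testing procedure are untouched. The point is worth acting on because the gap concerns the first ranked secondary endpoint and is cheap to close.

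**What to change.** Add a tipping-point run in which HAQ-DI values collected after premature discontinuation of study drug are set to missing before PROC MI, with the same shift grid. Zero shift then corresponds to the data set and the MAR assumption of the primary MMRM, although the analysis model remains ANCOVA on imputed data. Keep the AO run, labelled as supplementary to the AO ANCOVA. Report the number of off-drug Week 12 HAQ-DI values per arm, which shows at once whether the two runs can differ materially.

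The cost is one data step and one extra analysis. SAP section 11.1 says the primary efficacy analysis was completed under version 3.0 and that version 4.0 applies only to future long-term reporting. The run would therefore be an added post hoc analysis. Failing that, the report should say that the tipping point refers to the AO estimand.

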4.5 Data Monitoring Committee (DMC) Activities

An independent external Data Monitoring Committee (DMC) is used to review unblinded safety data at regular intervals during the conduct of the study. The DMC will provide recommendation to an AbbVie Point of Contact on whether to continue, modify, or terminate studies after each review. When needed, high-level unblinded efficacy data may also be requested by the DMC and be reviewed so that the DMC can assess benefit:risk of any emerging safety differences.

An unblinded interim efficacy analysis will also be conducted by an independent external DMC after at least 600 subjects have completed the Week 12 Visit or have prematurely discontinued from the study. The interim analysis is to assess if the study met the predefined No-Go boundary for the primary endpoint ACR20. A futility recommendation will be made only when both the upadacitinib 15 mg and 30 mg QD doses meet the futility criteria. To address potential practical regulatory and statistical concerns, a small alpha of 0.0001 will be spent for the interim analysis and the final analysis will be

performed at level 0.0499. The overall Type I error rate is controlled at 0.05. However, in no circumstance should a decision be made to stop the trial early for superiority in efficacy of ABT-494 versus either adalimumab or placebo. Details of the interim efficacy analysis are described in the DMC SAP and details of the decision making rules are specified in the DMC charter.

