9.2.3 Key Secondary Efficacy Analyses

The following is a list of ranked key secondary endpoints (upadacitinib versus placebo if not otherwise specified):

[figure not shown]
- 1. Change from baseline in HAQ-DI at Week 12;
- Static Investigator Global Assessment (sIGA) of Psoriasis of 0 or 1 and at least a 2-point improvement from baseline at Week 16 (for subjects with baseline sIGA ≥ 2);

- 3. Psoriasis Area Severity Index (PASI) 75 response at Week 16 (for subjects with ≥ 3% BSA psoriasis at baseline);
- 4. Change from baseline in modified PsA Sharp/van der Heijde Score (SHS) at Week 24;
- 5. Proportion of subjects achieving MDA at Week 24;
- 6. Proportion of subjects with resolution of enthesitis (LEI = 0) at Week 24 (for subjects with baseline presence of enthesitis (LEI > 0));
- 7. ACR 20 response rate at Week 12 (non-inferiority of upadacitinib vs adalimumab);
- 8. Change from baseline in SF-36 PCS at Week 12;
- 9. Change from baseline in FACIT-Fatigue at Week 12;
- 10. ACR 20 response rate at Week 12 (superiority of upadacitinib vs. adalimumab);
- 11. Proportion of subjects with resolution of dactylitis (LDI = 0) at Week 24 (for subjects with baseline presence of dactylitis (LDI > 0));
- 12. Change from baseline in Patient's Assessment of Pain NRS at Week 12 (superiority of upadacitinib vs. adalimumab);
- 13. Change from baseline in HAQ-DI at Week 12 (superiority of upadacitinib vs. adalimumab);
- 14. Change from baseline in Self-Assessment of Psoriasis Symptoms (SAPS) at Week 16.

Additional key secondary efficacy endpoints are:

- 1. ACR50/70 response at Week 12;
- 2. ACR20 response at Week 2.

[figure not shown]
Binary Endpoints

For binary endpoints, frequencies and percentages will be reported for each treatment group. For the ranked secondary endpoints at the time point of interest, the primary estimand is the same as that for the primary efficacy endpoint as defined in Section 9.2.1, except for the definition of the efficacy measurement.

For the key secondary endpoints applicable only for sub-population, the estimands will be constructed similarly but based on the sub-population, as defined in the below table.

Endpoint	Sub-population
Static Investigator Global Assessment (sIGA) of Psoriasis of 0 or 1 and at least a 2 point improvement from baseline at Week 16	Subjects with baseline sIGA ≥ 2 are included in the analysis

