9.2.5 Handling of Multiplicity

The overall type I error rate of the primary and ranked key secondary endpoints for the two doses will be strongly controlled using a graphical multiple testing procedure [1]. Specifically, the testing will utilize the endpoint sequence of primary endpoint followed by the ranked key secondary endpoints in the order as specified in Section 9.2.3, and will begin with testing the primary endpoint using $\alpha/2$ for each dose ($\alpha = 0.0499$ accounting for 0.0001 spending after interim futility analysis). Continued testing will follow a pre-

specified α transfer path which includes downstream transfer along the endpoint sequence within each dose as well as cross-dose transfer.

The graph for the testing procedures is provided in Figure 2. In the graph, the arrows specify the α transfer paths. Once an endpoint is rejected (i.e., deemed significant) at its assigned significance level, its significance level will be transferred to subsequent endpoint(s) following the arrow(s). The numbers on the arrows denote the weights for transferring significance levels. Specifically, the weight 1 denotes 100% transfer of significance level.

Figure 2. Graphical Multiple Testing Procedure

[figure not shown]

Figure 2. Graphical Multiple Testing Procedure (Continued)

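### The SAP places the Week 12 HAQ-DI tipping point at p > 0.05, a level its own multiplicity procedure never gives that test, so robustness may be overstated

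*SAP*

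**What the plan says.** SAP 9.2.3 puts HAQ-DI versus placebo at the head of the ranked key secondary endpoints ("1. Change from baseline in HAQ-DI at Week 12") and singles it out for a missing-data stress test: "For the key continuous endpoint change from baseline in HAQ-DI at Week 12, tipping point analysis will also be conducted using multiple imputation (MI").

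Appendix D describes that test. Missing values are imputed and then shifted separately in the upadacitinib and placebo groups, and the p-values are tabulated over a grid of shift pairs. The decision rule opens "If one pair of shift parameters are found to just reverse the study conclusion" and makes this concrete as "p-value larger than 0.05 (the original p-value < 0.05". It does not refer to the multiplicity procedure.

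The level for ranked conclusions is set elsewhere. SAP 4.5 states that "a small alpha of 0.0001 will be spent for the interim analysis and the final analysis will be" done at 0.0499. SAP 9.2.5 gives each dose half of that for the primary endpoint, "accounting for 0.0001 spending after interim futility analysis". Testing then follows an "α transfer path which includes downstream transfer along the endpoint sequence within each dose as well as cross-dose transfer". The transfer weights are in Figure 2, which is not shown in the text available.

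**The concern.** A tipping-point analysis asks how pessimistic the missing-data assumption must become before the finding is lost. The finding here is rejection of a ranked hypothesis at the level the graph gives it. If the rule waits for a p-value above 0.05, shift pairs whose p-value lies between the assigned level and 0.05 count as not yet tipped, although the hypothesis would no longer be rejected. The entry condition has the same fault: a result with p between the assigned level and 0.05 would be treated as a positive finding to be stress-tested, although it had failed its ranked test.

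Both faults act in one direction, towards making the first ranked secondary endpoint look more robust to data missing not at random.

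**Working it through.** **Inputs.** Interim spend 0.0001 and final level 0.0499 (SAP 4.5); half per dose at the start (SAP 9.2.5); tipping threshold 0.05 (SAP Appendix D); 410 subjects per upadacitinib group and 205 + 205 = 410 combined placebo (SAP 4.2); 10% dropout and an SHS effect size of 0.26 with about 90% power at two-sided 0.025 (SAP 4.3). The observed HAQ-DI z is not in the documents, so a range is used.

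**1. The plan's alpha.** 0.05 − 0.0001 = 0.0499, and 0.0499 / 2 = 0.02495. As a check, 0.0001 + 0.02495 + 0.02495 = 0.05. The split reproduces.

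**2. Sidedness.** If the per-dose level were one-sided, 0.05 two-sided would be nearly right. It is not. With 410 × 0.9 = 369 per group, 0.26 × √(369/2) = 3.53. Power at two-sided 0.025 is Φ(3.53 − 2.24) = 0.9015, which matches the stated figure of about 90%. Two-sided 0.05, or equally one-sided 0.025, gives 0.942. The Appendix D code tabulates the pooled p-value (Probt), which is also two-sided, so the two thresholds are on the same scale.

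**3. Levels HAQ-DI can receive.** If the primary endpoint hands its whole level down within the dose, HAQ-DI has 0.02495. If all alpha returns from the other dose, it has 0.0499, the total available. If the graph splits the primary endpoint's level, HAQ-DI could start below 0.02495; that case is not sized here.

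**4. Critical values (two-sided normal).** 0.05: 1.9600. 0.0499: 1.9608. 0.02495: 2.2422. The gap from 0.05 to 0.02495 is 2.2422 − 1.9600 = 0.2822 standard errors. The gap to 0.0499 is about 0.0009.

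**5. Overstatement of the tolerated shift.** With the standard error held constant, the erosion that can be absorbed is proportional to z − c, where c is the critical value. The overstatement is (z − 1.9600)/(z − c) − 1. At z = 3 and c = 2.2422 this is 1.0400/0.7578 − 1 = 37%.

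| Original z (assumed) | Level 0.02495 | Level 0.0499 |
|---|---|---|
| 2.5 | 109% | 0.16% |
| 3 | 37% | 0.08% |
| 4 | 16% | 0.04% |
| 5 | 10% | 0.03% |
| 6 | 7.5% | 0.02% |
| 8 | 4.9% | 0.01% |

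**6. The same gap in shift units.** Assume 410 per group, unit SD and a fraction m missing in each arm. The combined shift (upadacitinib worse plus placebo better) is then overstated by 0.2822 × √(2/410) / m at level 0.02495: 0.39 SD at m = 5%, 0.20 SD at 10% and 0.13 SD at 15%. At 0.0499 it is at most about 0.001 SD.

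**7. Entry condition.** An original z of 2.1 has p = 0.036. It meets the rule's condition with 0.14 standard errors to spare, yet it is 0.14 standard errors short of rejection at 0.02495.

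**The case against.** The strongest reply is that little depends on the label. The analysis is supplementary, and the HAQ-DI conclusion itself comes from the repeated-measures model in SAP 9.2.3 tested under the graph in 9.2.5. The p-value for every shift pair is tabulated, so a reader can apply any level without new computation. Nominal 0.05 also fits the SAP's general habit of reporting nominal p-values and 95% intervals beside the multiplicity-adjusted outcome. The first two points stand and limit the importance. The third explains the number but does not justify it, because Appendix D links the threshold to the study conclusion and not to nominal significance.

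A reader might infer that HAQ-DI is certainly tested at 0.02495 and that robustness is therefore overstated by the larger percentages. The documents do not support that. SAP 9.2.5 states 0.02495 as the starting level for the primary endpoint; what HAQ-DI receives depends on Figure 2 and on which hypotheses are rejected for the other dose. With full recycling the discrepancy all but disappears.

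The percentages are also approximate. Appendix D varies two shifts, truncates out-of-range values at the scale limits, and uses an ANCOVA on imputed data with sandwich errors, not the model behind the ranked test. A constant standard error and a linear effect of the shift are simplifications.

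**Conclusion.** The threshold is wrong as written, and the point is minor. Under the SAP's own allocation no single HAQ-DI test can be run above 0.0499, and nothing elsewhere in the SAP corrects the 0.05. The size depends on two things the documents do not give: the level HAQ-DI actually received and its original z. It ranges from negligible (full recycling, or a very strong effect) to material (level 0.02495 and a result near the boundary).

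A reader might also infer that the HAQ-DI claim or the family-wise error rate is compromised. Neither is. The tipping-point analysis feeds no ranked test and transfers no alpha. Nor do the documents show that any reported tipping point was in fact overstated, since they contain no results.

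**What to change.** In Appendix D, define the tipping point as the first shift pair, moving out from zero shift, whose p-value exceeds the level that the graphical procedure assigned to HAQ-DI for that dose: 0.02495 if the primary endpoint's full level passes down and none is recycled, and otherwise the level read from Figure 2 and the test outcomes. Apply the same level to the condition on the original p-value, and state the level beside the table.

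In the text this costs one sentence, and in the program one constant per dose. SAP 11.1 says the primary efficacy analysis was completed under version 3.0 and that version 4.0 governs only later long-term reporting, so editing the current SAP will not change the Week 12 output. The practical step is to re-mark the existing grid at the assigned level. No new imputation or modelling is needed, provided the grid extends to that boundary. The marked tipping point will come out the same or somewhat less favourable.
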